10.1 Risks of Tracheal Intubation in the ED or ICU

Patients who are severely ill enough to require emergency tracheal intubation in the ED or ICU as part of their clinical care are at high risk of complications. Many patients are undergoing intubation for hypoxemia or hemodynamic instability. Severe hypoxemia or cardiovascular instability occurs during nearly half of intubations in the ED and ICU (1, 2, 4, 5). Hypoxemia and hypotension during intubation are associated with an increased risk of cardiac arrest and death.(9, 10) Cardiac arrest occurs in 1-in-25 cases of emergency tracheal intubation.

Other complications during intubation may include aspiration (approximately 2.8% of cases), esophageal intubation (1.3%) injury to oral or dental structures (0.2%), and pneumothorax (0.1%). The long-term consequences of complications occurring during emergency tracheal intubation are unclear. Neurologic recovery from traumatic brain injury may be worse after hypoxemia due to secondary ischemic insult.(11)

10.2 Potential Risks of Participation in the PREOXI Trial

Participation in the PREOXI trial involves minimal incremental risk because:

- All patients eligible for the study are already experiencing emergency tracheal intubation, with the accompanying risks, as part of their clinical care
- Preoxygenation with non-invasive positive pressure ventilation and preoxygenation with facemask oxygen are both standard-of-care interventions that are commonly used in current clinical care. All patients eligible for the study would experience an approach to preoxygenation as part of their clinical care
- No benefits or risks are currently known to differ between the two approaches
- Both approaches have determined to be acceptable options for the optimal care of the patient by treating clinicians (otherwise the patient is excluded from the study)

Although no risks are currently known to differ between preoxygenation with non-invasive positive pressure ventilation and preoxygenation with facemask oxygen (both standard-of-care

approaches in currently clinical care), it is possible that the results of the PREOXI trial will ultimately demonstrate a difference between the two approaches in the risk of hypoxemia, hypotension, cardiac arrest, aspiration, or another outcome.

10.3 Potential Benefits of Participation in the PREOXI Trial

The primary benefits of the PREOXI trial will be the indirect benefits to society that would result if one approach to preoxygenation is found to prevent complications. Because millions of critically ill adults undergo emergency tracheal intubation each year, if one of the two approaches were found to prevent serious complications, the findings would immediately improve the care provided to millions of severely ill patients. Compared to the minimal risks of participation in the study, the pursuit of these benefits is reasonable.

10.4 Minimization of Risk

Federal regulations 45 CFR 46.111(a)(1) require that risks to patients are minimized by using procedures which are consistent with sound research design. This trial meets this human subjects protection requirement by incorporating numerous design elements to minimize risk to patients.

Both approaches to preoxygenation have been used in clinical practice for decades with an established safety profile in the same populations included in the PREOXI trial. To further mitigate risk, we will exclude patients with specific risk factors for adverse events such as those already receiving non-invasive positive pressure ventilation and any patient for whom treating clinicians determine that a specific approach to preoxygenation is required or contraindicated for the optimal care of the patient.

The trial protocol includes monitoring of adverse events, robust assessment of clinical outcomes, and an interim analysis by an independent DSMB, empowered to stop the trial or modify the trial protocol at any time.

Finally, to limit the risks associated with the collection of protected health information (PHI), the minimum amount of PHI necessary for study conduct will be collected. After collection, the data will be stored in a secure online database (REDCap) only accessible by the investigators. REDCap tools will be used to ensure that the PHI that is collected is only visible to investigators at the healthcare system where the patient was enrolled. To protect participant privacy, REDCap tools will be used to ensure that only deidentified data can be exported for use during analysis.

11. Statistical Considerations

11.1 Initial Sample Size Determination:

The minimum clinically important difference in hypoxemia that would be required to justify routine preoxygenation with non-invasive positive pressure ventilation rather than preoxygenation with facemask oxygen during emergency tracheal intubation of critically ill adults is uncertain. The current trial will be designed to detect a 6% absolute difference between groups in the rate of hypoxemia. An absolute difference of 6% in the incidence of hypoxemia is similar to or smaller than the difference considered to be clinically meaningful in the design of prior airway management trials.(19, 31) Assuming an incidence of hypoxemia of 17% in the facemask group based on data from two recently completed trials in the same ED and ICU

settings, detecting a 6% absolute decrease in the incidence of hypoxemia with 85% power at a two-sided alpha level of 0.05 would require enrollment of 1,264 patients (632 per group). Anticipating missing data for up to 3% of patients, we will plan to enroll a total of 1,300 patients (650 per group). This sample size calculation was performed in PS version 3.1.2.

11.2 Statistical Analysis:

Prior to the conclusion of enrollment, we will make publicly available a complete, final statistical analysis plan. Analyses conducted in accordance with the statistical analysis plan will be identified as *a priori*. Any additional analyses requested by the investigators or reviewers will be identified as *post hoc*.

11.2.1 Primary Analysis:

The primary analysis will be an unadjusted, intention-to-treat comparison of patients randomized to preoxygenation with non-invasive positive pressure ventilation versus patients randomized to preoxygenation with facemask oxygen with regard to the primary outcome. The difference between the two study groups will be compared using a Chi-squared test.

11.2.2 Secondary Analysis:

We will perform intention-to-treat comparisons of secondary, exploratory, and safety outcomes. Continuous outcomes will be compared with Wilcoxon Rank Sum test and categorical variables with the Chi-squared test. Data on patient characteristics will be summarized as number and proportion for categorical variables and as median and interquartile range for continuous variables.

We will also perform an adjusted comparison of the primary outcome between groups using a generalized linear mixed effects model including a random effect for site and fixed effects for group assignment and the following pre-specified baseline variables:

1. Age;
2. Sex;
3. Race and Ethnicity;
4. BMI;
5. Location at enrollment (ED or ICU)
6. Highest fraction of inspired oxygen in the hour prior to initiation of preoxygenation;
7. APACHEII score; and
8. Indication for intubation (hypoxic respiratory failure: Yes vs No)
9. Operator experience (number of previous intubations the operator has performed)

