8.3 Safety Outcomes

- Operator-reported aspiration
- Fraction of inspired oxygen at 24 hours after induction
- Oxygen saturation at 24 hours after induction
- New pneumothorax, defined as radiology report of new pneumothorax on chest imaging in the 24 hours after induction.
- New infiltrate, defined as radiology report of new infiltrate on chest imaging in the 24 hours after intubation.

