8.4 Exploratory Outcomes

- Procedural Characteristics & Complications
 - Severe hypoxemia (lowest oxygen saturation of <80%) between induction and two minutes after tracheal intubation
 - Very severe hypoxemia (lowest oxygen saturation of <70%) between induction and two minutes after tracheal intubation
 - Oxygen saturation at induction
 - Systolic blood pressure at induction
 - Duration from induction to successful intubation (duration of the intubation procedure)
 - Cormack-Lehane grade of glottic view on first attempt
 - Successful intubation on the first attempt
 - Number of laryngoscopy attempts
 - Number of attempts at passing a bougie
 - Number of attempts at passing an endotracheal tube
 - Cardiovascular collapse, defined as a composite of one or more of the following between induction and 2 minutes after intubation:
 1. Systolic blood pressure < 65 mmHg
 2. New or increased vasopressor
 3. Cardiac arrest not resulting in death within 1 hour of induction
 4. Cardiac arrest resulting in death within 1 hour of induction
- Clinical Outcomes
 - 28-day in-hospital mortality
 - Ventilator-free days to 28 days
 - ICU-free days to 28 days

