Data on pneumothorax and new pulmonary infiltrates are collected by study staff from clinical radiology reports using a structured case report form. The clinical radiologist who interprets the chest imaging is unaware of study group assignment. A lung infiltrate is considered to be present if the clinical radiologist identifies on the chest imaging the presence of air bronchograms, centrilobular nodules, consolidation, ground-glass opacity, infiltrate, opacity, parenchymal opacification, pneumonia, pneumonitis, pulmonary edema, or a tree-in-bud pattern. A pneumothorax or lung infiltrate present on chest imaging in the 24 hours after intubation will be assumed to be new if it was not present on chest imaging in the 24 hours prior to intubation. If no chest imaging is available in the 24 hours prior to intubation, any pneumothorax or lung infiltrate on chest imaging will be assumed to be new.

Primary Outcome

The primary outcome is the incidence of hypoxemia, defined as a peripheral oxygen saturation <85% during the interval between induction and 2 minutes after intubation.

We selected hypoxemia (as a binary variable) rather than lowest oxygen saturation (a continuous variable) as the primary outcome for the trial for several reasons. First, experiencing hypoxemia in the range associated with an increased risk of adverse clinical outcomes (e.g., cardiac arrest) may be more clinically relevant than changes in oxygen saturation within the normal range. For example a change in oxygen saturation of 5 percentage points from 87% to 82% may be more closely associated with adverse outcomes than a change in oxygen saturation of 10 percentage points from 100% to 90%. Second, values for oxygen saturation are “right-censored” because oxygen saturation reaches 100% with a partial pressure of oxygen in arterial blood (PaO_2) of approximately 100 mmHg but patients may have a higher PaO_2 following preoxygenation. The approach of analyzing hypoxemia as a binary variable rather than lowest oxygen saturation has been used by many prior trials and endorsed by airway experts.¹⁵⁻²⁰

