We will conduct unadjusted, intention-to-treat analyses comparing patients randomized to the noninvasive ventilation group versus the oxygen mask group with regard to all pre-specified safety, clinical, and exploratory outcomes. Continuous outcomes will be compared with the Wilcoxon rank sum test and categorical variables with the chi-square test. Between-group differences in continuous and categorical variables and the associated 95% confidence intervals will be presented.

Handling of missing data:

We anticipate that no patients will be lost to follow up before assessment of the primary outcome. In some cases, the oxygen saturation between induction and 2 minutes after intubation will be unmeasurable (e.g., poor plethysmography of pulse

oximetry, shock, cardiac arrest, peripheral arterial disease, or other reasons) or unavailable. We anticipate that data will be missing in less than 3% of cases based on the rates of missing data in prior trials in similar settings.^{25,26} Missing data will not be imputed for the primary outcome or for any of the secondary or exploratory outcomes. In adjusted analyses, missing data for baseline covariates will be imputed using multiple imputations.

Trial status:

PREOXI is a pragmatic, multi-center, non-blinded randomized clinical trial comparing preoxygenation with noninvasive ventilation to preoxygenation with an oxygen mask during the tracheal intubation of critically ill adults. Enrollment began on 10 March 2022 and is expected to conclude in 2023.

ETHICS AND DISSEMINATION

Waiver of Informed Consent:

Critically ill patients undergoing tracheal intubation in the ED or ICU are at significant risk for morbidity and mortality from their underlying illness. Most patients undergoing tracheal intubation in routine clinical care receive preoxygenation with either noninvasive ventilation or an oxygen mask. Any benefits or risks of these two approaches are experienced by patients undergoing tracheal intubation in clinical care, outside the context of research. As a requirement for enrollment in PREOXI, the patient's treating clinician must determine that either preoxygenation with noninvasive

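### Chi-square is the only test named for categorical safety and exploratory outcomes, with no rule for sparse tables such as pneumothorax or for the ordered glottic-view grade (minor, cheap to fix)

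*Combined protocol and SAP*

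**What the plan says.** Protocol v1.1 section 11.2.2 sets one rule for secondary, exploratory and safety outcomes: "Continuous outcomes will be compared with Wilcoxon Rank Sum test and categorical variables with the Chi-squared test". The SAP manuscript says the same under Analyses of Additional Outcomes: "Continuous outcomes will be compared with the Wilcoxon rank sum test and categorical variables with the chi-square test". It then adds "Between-group differences in continuous and categorical variables and the associated 95% confidence intervals will be presented", without naming the interval method. The published SAP gives chi-square as the general test for categorical variables under Statistical Analysis Principles, and refers the detail on additional outcomes to e-Appendix 1, which is not among the documents.

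Two outcomes matter here.

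- **Pneumothorax** is a safety outcome (section 8.3): "New pneumothorax, defined as radiology report of new pneumothorax on chest imaging in the 24 hours after induction". The only rate given is in section 10.1, which lists complications during intubation and includes "injury to oral or dental structures (0.2%), and pneumothorax (0.1" per cent). The SAP manuscript adds, under Data Collection, that without imaging in the 24 hours before intubation "any pneumothorax or lung infiltrate on chest imaging will be assumed to be new".
- **Glottic view** is an exploratory outcome (section 8.4): "Cormack-Lehane grade of glottic view on first attempt". Its test is not named separately.

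**The concern.** The chi-square P value is a large-sample approximation, and 0.1% of 650 patients is less than one event. Pneumothorax is also a harm that positive pressure could plausibly cause; section 14.4 uses a pneumothorax related to non-invasive ventilation as its example of a reportable event. If the analyst may choose between corrected, uncorrected and exact versions after seeing the table, the same few events can be reported on either side of 0.05.

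The interval matters too, because the SAP puts its weight for safety outcomes on estimates with 95% intervals. Protocol section 11.4 makes a similar statement but excepts safety analyses, so the documents do not clearly set safety P values aside.

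For the Cormack-Lehane grade the question is efficiency. The plan recognises only continuous and categorical outcomes, and an ordered grade fits neither label well.

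**Working it through.** **Inputs.** 650 per group, 17% versus 11%, 85% power and two-sided alpha 0.05 (protocol 11.1); pneumothorax 0.1% and aspiration 2.8% (protocol 10.1).

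**1. The plan's own figure.** With mean proportion 0.14 and difference 0.06, the uncorrected size is [1.960 × √(2 × 0.14 × 0.86) + 1.036 × √(0.17 × 0.83 + 0.11 × 0.89)]² / 0.06² = 599.0, or 600 per group after rounding up. The continuity-corrected size is (599.0/4) × [1 + √(1 + 4/(599.0 × 0.06))]² = 631.9, or 632. The stated 632 is therefore the continuity-corrected figure. The text does not say so.

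**2. Expected pneumothorax counts at 0.1%.** 650 × 0.001 = 0.65 per arm. No event in either arm: 0.999^1300 = 0.27. No event in at least one arm: 1 − (1 − 0.999^650)² = 0.77. Five expected events per arm would need a rate of 5/650 = 0.77%.

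**3. One sparse table, 0/650 versus 4/650.**
- Uncorrected chi-square: 1300 × (4 × 650)² / (650 × 650 × 4 × 1296) = 4.01, P = 0.045.
- Continuity-corrected: replace 4 × 650 by 4 × 650 − 650, giving 2.26, P = 0.133.
- Fisher, two-sided: 2 × C(650,4)/C(1300,4) = 0.124. Mid-P counts half the probability of each of these two extreme tables: 0.062.
- Wald interval for the difference: 0.62 ± 1.96 × 0.307 = 0.01 to 1.22 points. With a continuity correction of 1/650 (0.15 points): −0.14 to 1.37. Newcombe: −0.08 to 1.57.

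**4. The 0–0 table.** Chi-square divides by zero. A Wald interval has zero width. The Wilson upper limit for 0/650 is 1.96²/(650 + 1.96²) = 0.59%, so the Newcombe interval is −0.59 to +0.59 points.

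**5. True size at nominal 0.05,** by exact enumeration of two binomial arms with equal rates (a 0–0 table counts as no rejection). All rates except 0.1% and 2.8% are assumptions.

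| Rate | Expected per arm | P(0–0) | Uncorrected chi-square | Fisher |
|---|---|---|---|---|
| 0.1% | 0.65 | 27% | 0.0046 | 0.00006 |
| 0.2% | 1.3 | 7.4% | 0.024 | 0.0012 |
| 0.5% | 3.25 | 0.15% | 0.046 | 0.014 |
| 1% | 6.5 | about 0 | 0.044 | 0.025 |
| 2.8% (aspiration) | 18.2 | about 0 | 0.050 | 0.035 |

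**6. Glottic-view grade.** A 1-df test with 80% power has non-centrality 7.85. If the whole shift lies along the ordering, the same non-centrality on 3 df (four grades) gives 64.5% power. Simulation under four assumed grade distributions, with a common odds ratio of 1.35, gave power of 0.67 to 0.81 for Wilcoxon and 0.50 to 0.65 for chi-square. Chi-square rejected 0.046 to 0.051 of the time under the null.

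**The case against.** A reader might infer that these P values and intervals will be wrong or undefined, or that a chance handful of pneumothoraces would be reported as a significant harm. The documents do not support that, for these reasons, all of which stand.

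- **Size is not inflated.** At 0.1% the uncorrected chi-square test is very conservative. With equal rates of 0.1%, a split of 0 versus 4 or more, in either direction, has probability of only about 0.46%.
- **The significant result needs methods that the plan does not name.** It takes an uncorrected test and a Wald interval. The sample size matches a continuity-corrected formula; if the analysis is corrected too, 0 versus 4 gives P = 0.133 and an interval that includes zero.
- **The 0.1% is not the rate of the trial outcome.** It concerns complications during intubation. The outcome covers 24 hours of imaging and may count old findings as new. At 0.5% to 1% the uncorrected test is close to nominal.
- **Chi-square on an ordered grade is valid.** It gives up power, and its use for the grade is itself a literal reading of a general rule.
- **Little depends on the result.** The SAP favours estimates over significance for these outcomes, and no stopping or decision rule uses them.

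What these points leave is the omission itself. The visible text names no test for a table where chi-square cannot be computed, and does not say which version applies when the table is sparse. The missing e-Appendix 1 tempers certainty, but the SAP manuscript's own section on additional outcomes repeats the general rule.

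**Conclusion.** The point holds as a gap in specification, of minor severity. At the only rate the protocol supplies, the only named test has a 27% chance of being undefined for pneumothorax, and individual sparse tables can fall on either side of 0.05 according to a choice the plan leaves open. This rests on the 0.1% applying to the 24-hour outcome. The problem shrinks as the rate rises: at about 0.77%, five events per arm are expected. Because no interval method is named, the zero-width interval is a risk and not a demonstrated error. For the Cormack-Lehane grade the cost is about 15 points of power on one exploratory outcome (80% to about 65%), if the shift follows the ordering and the general rule is taken literally. Aspiration at 2.8% is adequately served by chi-square, and the primary analysis is unaffected.

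**What to change.** Add to protocol 11.2.2 and the SAP:

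- When any expected count is below 5, use Fisher's exact test or its mid-P version. Name one of them in advance, since at 0 versus 4 they differ (0.124 and 0.062).
- Use score-type intervals (Newcombe or Miettinen-Nurminen) for differences in sparse proportions. These are defined even with no events.
- Compare Cormack-Lehane grade with the Wilcoxon rank-sum test already planned for continuous outcomes.

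The cost is a sentence or two and standard software. Fisher's test is conservative (size 0.014 against 0.046 for chi-square at an assumed 0.5%), which is a reason to consider mid-P. If pneumothorax proves more frequent, the small-count rule does not come into play and nothing is lost.

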11.2.3 Effect Modification (Subgroup Analyses)

To evaluate whether pre-specified baseline variables modify the effect of study group assignment on the primary outcome, we will perform logistic regression modelling with the primary outcome as the dependent variable and independent variables of study group, the proposed effect modifier, and the interaction between the two. Any interaction term with a p-value less than 0.1 will be considered to identify an effect modifier. To account for non-linear relationships, continuous variables will be analyzed using restricted cubic splines with between 3 and 5 knots. Forest plots will be used to graphically display the adjusted analyses, and locally weighted regression or partial effects plots will be used to portray the association between continuous

covariates and the outcome. A full list of prespecified subgroup analyses will be outlined in the detailed Statistical Analysis Plan but will include:

1. BMI;
2. Location (ED vs ICU);
3. Highest fraction of inspired oxygen in the hour prior to initiation of preoxygenation)
4. Indication for intubation (hypoxic respiratory failure, other) ;
5. APACHEII score; and
- 6.

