11.4 Correction for Multiple Testing

We will analyze a single pre-specified primary outcome and a single pre-specified secondary outcome. Consistent with recommendations of the Food and Drug Administration⁶⁰ and the European Medicines Association,⁶¹ each will be tested using a two-sided P value with a significance level of 0.05. For all other analyses except safety analyses, emphasis will be placed on the estimate of effect size with 95% confidence intervals, as recommended by the *International Committee of Medical Journal Editors*,⁶² and no corrections for multiple comparisons will be performed.

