Exploratory clinical	28-d in-hospital mortality.
	Ventilator-free days to 28 d.
	ICU-free days to 28 d.

Sample Size Estimation

The current trial is designed to detect a 6% absolute difference between groups in the incidence of hypoxemia, a difference that is similar to or smaller than the difference considered to be clinically meaningful in the design of prior trials of oxygenation strategies during tracheal intubation.^{2,15} Assuming an incidence of hypoxemia of 17% in the oxygen mask group based on data from two recently completed trials by this network in similar ED and ICU settings, detecting a 6% absolute decrease in the incidence of hypoxemia with 85% power at a two-sided α level of .05 would require enrollment of 1,264 patients (632 per group).^{16,17} Anticipating missing data for up to 3% of patients, we plan to enroll a maximum of 1,300 total patients (650 per group). This

sample size calculation was performed in PS version 3.1.2 software (Vanderbilt University Medical Center).

Data and Safety Monitoring Board and Interim Analysis

The data and safety monitoring board and interim analysis are described in [e-Appendix 1](#).

Statistical Analysis Principles

Analyses will be conducted following reproducible research principles using R software (R Foundation for Statistical Computing). Categorical variables will be presented as number and percentage and will be compared between groups using a χ^2 test. Continuous variables will be presented as mean \pm SD or median

(interquartile range) and will be compared between groups using a Wilcoxon rank-sum test. We will present absolute between-group differences with associated 95% CIs. A two-sided P value of $< .05$ will define a statistically significant between-group difference in the primary outcome. With a single primary outcome, no adjustment for multiplicity will be made. For secondary, safety, and exploratory analyses, emphasis will be placed on the magnitude of differences between groups with 95% CIs, rather than statistical significance.

Main Analysis of the Primary Outcome

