The main analysis will be an unadjusted intention-to-treat comparison of the primary outcome of hypoxemia between patients randomized to the noninvasive ventilation group vs patients randomized to the oxygen mask group using a χ^2 test. The absolute difference in proportions, associated 95% CI, and a P value for the comparison will be presented. The primary analysis will be conducted among patients for whom the primary outcome is available without imputation of missing data. Planned tables of baseline characteristics, procedural characteristics, and outcomes are presented in e-Tables 2 and 3.

Additional Analyses of the Primary Outcome

Multivariable Analysis: To account for relevant baseline covariates, we will fit a generalized linear mixed effects model using a logit link function with the primary outcome as the dependent variable, study site as a random effect, and fixed effects of study group and the following prespecified baseline covariates: age, sex, race and ethnicity, BMI, location at enrollment (ED or ICU), highest FIO_2 1 h before initiation of preoxygenation, Acute Physiology and Chronic Health Evaluation II score,¹⁸ indication for intubation (hypoxemic respiratory failure: yes vs no), and operator experience (number of previous intubations the operator has performed). All continuous variables will be modelled assuming a nonlinear relationship to the outcome using restricted cubic splines with between 3 and 5 knots.

Effect Modification: We will examine whether prespecified baseline variables modify the effect of study group assignment on the primary outcome using a formal test of statistical interaction in a logistic regression model with the primary outcome as the dependent variable and independent variables of study group, the proposed effect modifier, and the interaction between the two. For categorical variables, we will present the OR and 95% CIs within each prespecified subgroup. Continuous

variables will not be dichotomized for analysis of effect modification, but may be dichotomized for data presentation. In accordance with the Instrument for Assessing the Credibility of Effect Modification Analyses recommendations, we have prespecified the following baseline variables as potential effect modifiers and hypothesized the direction of effect modification for each.

Patient Location (ED vs ICU): We hypothesize that patient location will not modify the effect of study group assignment on the primary outcome.

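### Do the protocol's p < 0.1 label for effect modifiers and the SAP's loose FiO2 wording call for a change to the subgroup plan?

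*Combined protocol and SAP*

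**What the plan says.** Protocol v1.1, section 11.2.3, tests each modifier in a logistic model containing study group, the modifier and their interaction. It adds the rule "Any interaction term with a p-value less than 0.1 will be considered to identify an effect modifier" and says that "continuous variables will be analyzed using restricted cubic splines with between 3 and 5 knots". It lists five modifiers (BMI, location, FiO2, indication for intubation and APACHE II) and defers the full list to the SAP. The rule is unchanged from protocol v1.0.

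Protocol section 11.4 covers everything other than the primary, secondary and safety analyses. There, "emphasis will be placed on the estimate of effect size with 95% confidence intervals" and "no corrections for multiple comparisons will be performed". Section 11.2 makes the SAP the reference for prespecification: "Analyses conducted in accordance with the statistical analysis plan will be identified as" a priori.

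The published SAP (Effect Modification) examines the same five modifiers "using a formal test of statistical interaction in a logistic regression model". The preprint SAP does so in a mixed model with site as a random effect. Both cite ICEMAN and give a hypothesis for each modifier: location and APACHE II are expected not to modify the effect, and the other three are expected to, in a stated direction. Neither sets a p-value threshold. The published SAP's Statistical Analysis Principles say that for secondary, safety and exploratory analyses "emphasis will be placed on the magnitude of differences between groups with 95% CIs, rather than statistical significance".

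For FiO2, protocol 11.2.3 defines the modifier as "Highest fraction of inspired oxygen in the hour prior to initiation of preoxygenation". The adjusted-model covariate in both SAP texts is also tied to the start of preoxygenation. The SAP's FiO2 modifier is tied to the hour before intubation instead.

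**The concern.** Two things look wrong.

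First, the protocol applies a yes/no label at a looser level than the 0.05 used for the primary outcome, while section 11.4 and both SAP texts lean on estimates with confidence intervals. An interaction with p = 0.08 would be a named effect modifier under 11.2.3 and only an estimate with its interval elsewhere. Version 1.1 was issued to align the protocol with the SAP, so the sentence reads like a leftover. It also refers to any interaction term, whereas a spline with 3 to 5 knots has 2 to 4 such terms per continuous modifier, and nothing states outright that one joint test per modifier is meant.

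Second, a literal hour before intubation overlaps the randomized preoxygenation. The SAP recommends FiO2 of 100% during noninvasive ventilation and says that oxygen masks may yield alveolar concentrations as low as 50%. A modifier measured in that window would depend on assignment, and its interaction with assignment would be hard to interpret.

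At stake are the exploratory subgroup claims only.

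**Working it through.** **The plan's own figure.** The documents give no error rate for the interaction tests. The nearest figure to reproduce is the sample size, which sets the scale for the power example below. Inputs from section 11.1: 17% vs 11%, two-sided 0.05, 85% power.

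- Without continuity correction: (1.960 × √(2 × 0.14 × 0.86) + 1.036 × √(0.17 × 0.83 + 0.11 × 0.89))² / 0.06² gives 600 per group after rounding up.
- With continuity correction: 632 per group, 1,264 in total, which matches the plan.
- Evaluable patients: 1,300 × 0.97 = 1,261.

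**False labels, one test per modifier at 0.1.** If k modifiers are null and the tests are independent, the chance of at least one false label is 1 − 0.9^k. The expected number is 0.1k, whatever the correlation.

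| Null modifiers | At 0.1 | Expected false labels at 0.1 | At 0.05 |
|---|---|---|---|
| All five | 1 − 0.9^5 = 0.410 | 0.5 | 1 − 0.95^5 = 0.226 |
| Location and APACHE II only | 1 − 0.9^2 = 0.190 | 0.2 | 1 − 0.95^2 = 0.0975 |

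**Simulation with joint tests.** All distributions are assumed; each setting used 1,500 trials.

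- 1,261 patients, independent modifiers: at least one p < 0.1 among five null modifiers in 0.41 of trials (3 knots) and 0.39 (5 knots).
- 1,260 patients, 12 scenarios, correlation up to 0.8 among FiO2, APACHE II and indication: 0.375 to 0.443 for five. Counting location and APACHE II only: 0.179 to 0.217.
- The Monte Carlo standard error is about 0.013 for five modifiers. The top value of 0.443 is therefore about 2.6 standard errors above 0.410; the reason was not established. The gap of 0.03 does not alter the conclusion.

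**Per-coefficient reading.** Two binary modifiers plus three continuous ones with 2 to 4 terms each give 2 + 3 × 2 = 8 to 2 + 3 × 4 = 14 terms. In the first simulation at least one term had p < 0.1 in 0.48 (3 knots) and 0.56 (5 knots) of trials.

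**What the 0.1 level buys.** Assume a 50/50 modifier, 315 patients per cell (4 × 315 = 1,260), and a two-fold ratio of odds ratios. Event rates are 17% in both mask cells and 14.9% and 8.0% in the noninvasive ventilation cells.

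- SE of the interaction log odds ratio: √Σ[1/(315 × p(1 − p))] = √(0.0225 + 0.0225 + 0.0250 + 0.0431) = 0.336.
- z = ln 2 / 0.336 = 2.06.
- Power at 0.1: Φ(2.06 − 1.645) = 0.66.
- Power at 0.05: Φ(2.06 − 1.960) = 0.54.

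**FiO2, texts side by side.**

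| Source | Anchor |
|---|---|
| Protocol 11.2.3, modifier | Start of preoxygenation |
| Both SAP texts, covariate | Start of preoxygenation |
| Both SAP texts, modifier | Intubation, but introduced as a baseline variable |
| Protocol section 9, data collected | Highest in the hour before enrollment; value at enrollment; value at 24 hours |

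Section 9 lists no FiO2 between enrollment and intubation, so the post-randomization reading could not be carried out with the listed variables. The SAP's rationale concerns patients who require more oxygen, which is a patient characteristic and not an effect of the assigned device.

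**The case for a change.** The case for a change is that two governing texts handle the same test differently, and a reader cannot tell whether an interaction at p = 0.08 will be named. Editing costs nothing but words: delete the sentence or repeat it in the SAP, state one joint test with fixed knots, and use one FiO2 definition. A per-coefficient reading would raise the all-null false-label rate to about 48–56%.

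Part of this stands. The texts do differ, and identical wording would be tidier. But a stated threshold and a silent SAP do not contradict each other, and the version log claims only that the subgroup variables were aligned, not the decision rule. Section 11.4 asks for emphasis on estimates, and a label can sit beside an estimate and its interval. Deleting the rule would leave a formal test with no criterion fixed in advance and would give up sensitivity. The per-coefficient reading is strained, because 11.2.3 speaks of the interaction between group and modifier; a joint test is what an analyst would run. For FiO2, the SAP's complete variable list is in a supplement that was not available here, so a post-randomization variable cannot be strictly excluded. Nothing in the supplied texts points to one.

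**Conclusion.** No change is needed. The 0.1 rule is a prespecified trade-off in exploratory analyses for which the plan openly declines multiplicity correction. On the SAP's own hypotheses it carries about a 19% chance of at least one false label. The 41% figure needs all five modifiers to be null and independently tested, which the SAP does not expect. Against that, power rises from about 54% to 66% in the assumed two-fold example. If the SAP is the operative text, as section 11.2 suggests, the label does not apply and neither error rate arises.

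The joint test and the number of knots are details that analysts fill in sensibly. The FiO2 anchor is loose wording, and the baseline description and the listed data settle it; the documents give no basis for sizing any distortion. These conclusions assume one joint test per modifier and a pre-enrollment FiO2 value. The primary and secondary outcome analyses do not depend on any of this.
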